# 2.2 STUDY RATIONALE

To date, a number of studies have been carried out on the first generation of the OLANI measuring PK, efficacy and safety data. The current study seeks to collect pilot PK data on the second generation OLANI in healthy participants without a DSM 5 - Substance Related Disorders classification. The use of healthy non-substance dependent volunteers for this protocol greatly reduces the risk of opioid withdrawal related AE's and opioid overdose due to sub-therapeutic naltrexone blood levels being recorded. This pilot data will be used in the planning and design of a large bioequivalence study on the OLANI.

# 2.3 POTENTIAL RISKS AND BENEFITS

#### 2.3.1 Known Potential Risks

- 1. When the local anesthetic used during OLANI insertion wears off, the site of implantation may be tender.
- 2. The OLANI may cause irritation or inflammation at or near the site of administration as a result of an allergic response or other inflammatory process.
- 3. There is a risk of infection with any surgical procedure of this type. The risk is minimized by use of appropriate sterile technique and ensuring that the formulation meets normal pharmaceutical standards for sterility.
- 4. In the unlikely event the participant requires narcotic painkillers for severe pain; most will have a greatly reduced effect whilst naltrexone is still being released from the OLANI and higher doses of high potency opioids may need to be used. In instances where pain cannot be controlled by other means (such as regional blocks or alternative drugs see section 7.7) the OLANI may have to be removed surgically.

- 5. Known side-effects from naltrexone include difficulty sleeping, anxiety, nervousness, abdominal pain/cramps, nausea and/or vomiting, low energy, join and muscle pain, headache, loss of appetite, diarrhea, constipation, increased thirst, increased energy, depressive mood, irritability, dizziness, skin rash, delayed ejaculation, erection dysfunction, reduced sexual desire, and chills.
- 6. Naltrexone has been associated with reversible hepatocellular injury indicated by elevated liver enzymes when administered at doses substantially greater than the doses expected in this study. When used in the lower dose range in opiate dependent patients, this risk is remote. Naltrexone is therefore contraindicated in participants with acute hepatitis or liver failure, and such participants are excluded from the study. Participants with hepatic enzyme levels greater than three times the upper limit of normal are excluded. Implantable naltrexone achieves lower blood levels than oral naltrexone initially, and blood level should remain lower throughout treatment period than levels associated with hepatitis. If naltrexone induced hepatitis were to occur in the setting of long-acting preparation, where the naltrexone would be only very slowly eliminated, this would prolong exposure to the offending agent. However, the experience with injectable and implantable naltrexone also suggests it is safe. In studies with injectable naltrexone several participants experienced elevation in liver enzymes, which were determined to be related to hepatitis C. Several recent reports with injectable naltrexone showed that it poses significantly lower risk of hepatotoxicity than previously suspected, even among alcohol and opioid-dependent persons including those with HCV and/or HIV infection. In July of 2013, the Boxed Warning on the hepatotoxicity was removed from the Vivitrol Package Insert."
- 7. Naloxone injection may cause withdrawal symptoms such as nausea, vomiting, diarrhea, stomach pain, fever, sweating, body aches, weakness, running nose, goosebumps, shivering, increased heart rate, and anxiety.

#### 2.3.2 Known Potential Benefits

- 1. There are no known potential benefits of this treatment in the study cohort.
- 2. There is a large potential benefit to the opiate addicted community should the PK pilot study provide strong pharmacokinetic data which would aid in getting a long term naltrexone product through the registration process and onto the market.

#### **3 OBJECTIVES AND PURPOSE**

#### **3.1 PRIMARY OBJECTIVES**

To characterize the pharmacokinetic profile ( $C_{max}$ ,  $T_{max}$ , AUC, T>MEC, where MEC = 1.33 ng/mL NTX, Time to  $C_0$  for naltrexone) of the OLANI (2 units).

Primary outcomes used to determine these properties will be based on results from plasma concentration of naltrexone and 6- $\beta$ -naltrexol as ascertained from blood samples taken at the following time points:

- 0, 3, 6, 12, 24, 48 hours
- 4, 8, 14, 21, 28, 35, 42, 49, 56, 90, 120, 150, 180, 210, 240, 270, 300, 330, 360, 390, 420, 450, 480, 510 & 540 days.

Note: 1.33 ng/mL is a target MEC for this protocol. The MEC will be further developed over time.

#### **3.2 SECONDARY OBJECTIVES**

• To characterize the safety profile (i.e. AEs, laboratory results, wound site and inflammatory response rates) of the OLANI.

# **4 STUDY DESIGN AND ENDPOINTS**

#### 4.1 DESCRIPTION OF THE STUDY DESIGN

This pilot study is a phase I/II, open label, single-arm pharmacokinetic trial of the OLANI in healthy participants without a DSM 5 - Substance Related Disorders classification. PK data will be collected in all participants until 2 consecutive monthly naltrexone blood levels recorded at <0.1 ng/mL, it is anticipated that this will occur by Day 540. Participants will be required to undergo a Naloxone Challenge Test (NCT) to confirm absence of physiological dependence on opioids before administration of the study medication. Participants will be recruited, treated and followed up at the SURC clinic at the NYSPI.

All participants will be treated with a double administration of a 1.8g ( OLANI.

#### 4.2 STUDY ENDPOINTS

#### 4.2.1 Primary Endpoint

• The collection of at least 75% pharmacokinetic blood time points including 2 consecutive monthly naltrexone blood levels recorded at <0.1 ng/mL, in 10 participants.

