#### 5.3 STRATEGIES FOR RECRUITMENT AND RETENTION

#### 5.3.1 Target Sample Size:

A total of 20 participants (10 females and 10 males) will be recruited. We expect that 10 of the 20 participants will complete the study (50%), which is providing at least 75% valid pharmacokinetic blood samples including 2 monthly naltrexone blood levels recorded at <0.1 ng/mL.

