#### 7.2.3 Total amount of Blood to be collected

The amount of blood drawn for the study is:

- HIV and Hepatitis screening = 10 mL.
- FCP and FBC = 180.5 mL (18 x 9.5 mL)
- Pregnancy testing (Female participants only) = 4 mL (during the trial, a blood test will be used to confirm a positive urine result)
- Total blood samples for naltrexone / naltrexol =  $288 \text{ mL} (32 \times 9 \text{ mL})$
- There is also the potential for further bloods to be taken on any un-scheduled visit for PK bloods (10 mL) and follow-up visit for outstanding AEs (FCP and FBC 9.5 mL) post end of trial.

**Note:** that the total blood samples for naltrexone / naltrexol have been calculated for the worst case of participants going out to Day 540. In the event that a participant registers two consecutive monthly naltrexone blood levels recorded at <0.1 ng/mL, then the participant will be withdrawn from the study and the blood collection will be reduced by 10 mL for every monthly time point not required.

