#### A PILOT PHARMACOKINETIC TRIAL OF THE O'NEIL LONG ACTING NALTREXONE IMPLANT CONFIDENTIAL Go-Medical Protocol GM0017: (Ver. 0.13; 11 June 2020)

	Screening Visit 1 	Screening Visit 2 	Recruitment Visit 	Admission Day -1 	Admission Day 0 	Admission Day 1 & 2 	Day 4  (±1 day)	Day 8  (±2 days)	Day 14, 21, 35, 42 & 49  (±3 days)	Day 28 & 56  (±3 days)	Monthly PK Visit  (±10 days)	Final Visit 	Early Termination / Withdrawal 	Un- scheduled Visit 	PK Follow- up 	AE Follow- up 
AE Monitoring		X	X	Х	X	х	X	X	Х	X	Х	X	Х	Х	X	X
Urine Drug Screen		X		Х						Х	Х	Х			Х	
Recent Drug Use- Baseline (RDU)		X														
Quantitative Substance Use Inventory	2 2			X						X	X	X		Х	X	
Naloxone Challenge Test			24  0	Х	2		2 2								S	- (s 2-
COWS Baseline, 10 Minutes, 20 Minutes, 30 Minutes				х				~ ~ ~ ~ ~ ~ ~ ~ ~ ~ ~ ~ ~ ~ ~ ~ ~ ~ ~								
Subcutaneous Implant (Dosing) EX	2°				Х								6. 10		2. 3	
Vital Signs (Height, Weight, BMI)	Х	1											83	28 N		
Vital Signs with weight 					Х		Х	X	Х	Х	X	Х	Х	Х	Х	Х
Wound Site/ Implant Site Assessment						X6	X	X	X	x	x	X	x	х	x	

1. Inclusion/exclusion criteria will only be reviewed at Screening Visit 2 and the Recruitment Visit.

2. C-SSRS will be used to assess suicidal risk. Lifetime risk will be assessed at screening visit 1, with subsequent visits assessing risk since last visit (SLV).

3. A blood sample will be taken for NTX & 6BN at Screening Visit 2.

4. Pregnancy testing will be conducted on all females of child bearing potential on serum at screening, subsequent testing will be carried out on urine samples with serum testing used to confirm positive urine results as per section 7.2.1.

5. Initial 48 hours PK Sampling - Blood samples will be collected at the following time points: Baseline screening visit, 3 hour ±60 min, 6 hour ±60 min, 12 hour ±60 min, 24 hour ±2 hours and 48 hour ±2 hours after the implant procedure. The actual time of each PK sample collection should be recorded.

6. Wound site/implant site assessment for day 1 (24h) and day 2 (48) will take place within ±2hours.

7. Monthly PK visit - Blood samples will be collected at the following time points: Day 90, 120, 150, 180, 210, 240, 270, 300, 330, 360, 390, 420, 450, 480, 510 & 540.

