#### A PILOT PHARMACOKINETIC TRIAL OF THE O'NEIL LONG ACTING NALTREXONE IMPLANT CONFIDENTIAL Go-Medical Protocol GM0017: (Ver. 0.13; 11 June 2020)

- 12. Satellite Location 1 = Columbia University Medical Center (CUMC), [name]
- 13. Satellite Location 2 = Clinilabs, [name] for all visits after the initial 48-hour time-point
- 14. Changes Due to COVID-19: During the public health emergency, some of the monthly follow-up visits may occur by telephone/video only. The following safety assessments will occur during these remote study visits: concomitant medication review, PHQ (BDI-II), C-SSRS1 (since last visit), AE monitoring, Qualitative Substance Use Inventory and wound site/implant site assessment (self-reported) done via video link, if possible. Conversely, the following assessments/procedures may be missed because of having remote study visits: safety labs, PK blood collection, pregnancy test, urine drug screen, vital signs/weight.
- 15. Unscheduled Visits: Vital signs, concomitant medication review, wound site/implant site assessment and AE monitoring are to occur at all Unscheduled Visits. Additional assessments performed are at the discretion of a study physician.
- 16. Vital Signs: Blood pressure, heart rate, respiratory rate, and oral body temperature will be measured after the subject has been in a seated position for at least 5 minutes. Note: After a subject's last visit, the Disposition CRF must be completed.

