#### 10.4.7.2 Efficacy Review

An interim analysis will be carried out once at least 10 participants have completed their Day 180 PK blood time point. Participants, who submitted at least 14 of 19 valid blood samples (including the Day 180 sample) and safety data will be evaluated whether or not they met the MEC criteria (naltrexone blood level above 1.33 ng/mL). The analyzed interim data will be used in the planning and design of a bioequivalence/safety study of the OLANI against a reference extended release naltrexone product.

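### The completer rule leaves its 75% denominator, the placing of missed draws and the meaning of consecutive open, and this decides who is counted and analysed

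*Combined protocol and SAP*

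**What the plan says.** Section 4.2.1 defines the primary endpoint as "The collection of at least 75% pharmacokinetic blood time points including 2 consecutive monthly naltrexone blood levels recorded at <0.1 ng/mL, in 10 participants". Sections 10.4.2 and 10.5 repeat the condition, and 10.4.2 makes it the entry rule for the analysis. Section 10.3 takes the 75% over *applicable* time points without defining the word.

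Section 5.3.1 describes a completer as "providing at least 75% valid pharmacokinetic blood samples including 2 monthly naltrexone blood levels recorded at <0.1 ng/mL", without *consecutive*. Section 7.3.6 schedules the Final Visit after two non-detectable samples or after Day 540, also without *consecutive*. Sections 4.1 and 7.2.3 tie the end of sampling to two consecutive monthly levels. Section 7.3.9 says a visit may follow Day 540 if naltrexone is detectable, then says such visits go on until a consecutive pair is recorded. Table 7-1 note 8 defines undetectable as below 0.1 ng/mL.

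Missed draws are foreseen. Under note 14, "the following assessments/procedures may be missed because of having remote study visits: safety labs, PK blood collection". The one place where a particular draw is required is the interim analysis in 10.4.7.2: "Participants, who submitted at least 14 of 19 valid blood samples (including the Day 180 sample".

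**The concern.** A percentage of draws says how many samples exist, not where they lie. Nearly half of this schedule falls in the first 56 days, so a participant can reach 75% with a long stretch of the monthly phase unobserved. That phase is where the level is expected to fall through 1.33 ng/mL. AUC and time above 1.33 ng/mL (T>MEC) are primary-objective parameters in 3.1. The efficacy endpoint in 4.2.3 is judged on the levels that were collected, so a missed draw can never count against a participant.

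The washout half of the rule has the opposite weakness. If a missed draw breaks the sequence, someone whose washout has been observed may not count. The sections do not settle whether it does. With 10 completers wanted from 20 recruited, a few such cases matter.

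**Working it through.** **Inputs.** Section 3.1 lists six early points ("0, 3, 6, 12, 24, 48 hours"), then Days 4 to 56, which is nine points. Table 7-1 note 7 lists 16 monthly points ("Day 90, 120, 150, 180, 210, 240, 270, 300, 330, 360, 390, 420, 450, 480, 510 & 540").

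- Total: 6 + 9 + 16 = 31, of which 6 + 9 = 15 fall by Day 56.
- By Day 180: 15 + 4 = 19, which reproduces the 19 in 10.4.7.2.
- Recruitment: 10 / (1 - 0.50) = 20, which reproduces 5.3.1.
- The line "Total blood samples for naltrexone / naltrexol" in 7.2.3 budgets 32 samples, one more than the schedule. The Final Visit draw in Table 7-1 may account for it.

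**Gaps, denominator up to the participant's stop.** Suppose Days 90, 120, 150, 180 and 210 are missed and Days 240 and 270 are both below 0.1 ng/mL.

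- Points scheduled to Day 270: 15 + 7 = 22. Collected: 22 - 5 = 17.
- 17/22 = 77.3%, so the participant is complete.
- Unobserved interval: 240 - 56 = 184 days. If the Day 56 level is above 1.33 ng/mL, T>MEC is known only to lie between Day 56 and Day 240.

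**Seven missed draws.** With Days 90 to 270 missed, the hole is 300 - 56 = 244 days.

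- Denominator up to the stop: a last draw at Day 420 gives 20/27 = 74.1% (fails); at Day 450 it gives 21/28 = 75.0% (passes).
- Fixed 31: 0.75 x 31 = 23.25, so 24 draws are needed. 31 - 7 = 24 (77.4%) is reached only with sampling to Day 540.

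**Is this compatible with a plausible decline?** As an assumption, take C(t) = P exp(-(t/τ)^k) with plateau P = 6 ng/mL, k = 3 and T>MEC = 150 days. The level reaches 0.1 at 150 x [ln(60)/ln(6/1.33)]^(1/3) = 150 x (4.094/1.507)^(1/3) = 209 days. Missing Days 90 to 210 then gives a pair at Days 240 and 270, and 17/22 passes. Missing Days 90 to 270 gives a pair at Days 300 and 330, and 17/24 = 71% fails.

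**Full attendance, fixed denominator.** A participant whose pair falls at Days 270 and 300 has 15 + 8 = 23 draws. 23/31 = 74.2%, which fails with nothing missed. With 32 points and the Final Visit draw counted, 24/32 = 75.0% passes. The undefined denominator alone decides the outcome.

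**Interim.** 14/19 = 73.7%, and a strict 75% would need 15. Requiring Day 180 still lets Days 49, 56, 90, 120 and 150 be missing, a hole of 180 - 42 = 138 days.

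**Washout pair.**

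- One missed draw: below 0.1 at Day 390, Day 420 missed, below 0.1 at Day 450. If sampling continues, Day 480 completes an adjacent pair. When the first washed-out level is at Day 450 or earlier, this can be done by Day 540; from Day 480 on it needs Day 570 or later.
- Two missed draws: below 0.1 at Days 450 and 540, with Days 480 and 510 missed. With all else collected, 29/31 = 93.5%. On the strict reading 4.2.1, 10.4.2 and 10.5 are not met, while 5.3.1 is. Section 7.3.6 ends follow-up, and the opening condition of 7.3.9 (detectable naltrexone) is not met.
- Spacing: with windows of ±10 days, adjacent monthly draws can fall on Days 310 and 320 (300 + 10 and 330 - 10), only 10 days apart.

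**The case against.** A reader might infer that a seven-month block of missed draws routinely counts as complete. The documents do not support that, because sampling stops at the washout pair and most people would stop too early for seven misses to pass. For 36 assumed profiles of the form above (plateau 2.5, 4 or 6 ng/mL; T>MEC 150, 200 or 260 days; shape 1.5, 2, 3 or 4), with Days 90 to 270 missed, 1 of 36 reaches 75% of 31 and 8 of 36 reach 75% of points up to the stop. The five-draw case is the one to rely on.

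A reader might also infer that one missed draw between two washed-out levels makes a participant incomplete. Sections 4.1 and 7.3.9 point the other way: sampling continues until an adjacent pair is recorded, and the usual cost is one more draw. What remains is narrower. Section 7.3.6 and the detectability condition in 7.3.9 can close follow-up before that draw is taken. The Final Visit draw might complete the pair, but nothing says whether it counts as a monthly level.

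Nor do the documents record a long run of missed draws. Remote visits began on 27 April 2020, the protocol version is dated 11 June 2020, and note 14 says only that some monthly visits may be remote. The 10-day spacing needs opposite extremes of two windows.

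Finally, this is a descriptive pilot with no hypotheses, the endpoint is a data-collection count, and individual profiles are plotted and tabulated (10.4.3, 10.4.10), so gaps will be visible. That is fair, and it limits the severity. It does not say who is counted toward the ten or enters the 10.4.2 analysis.

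**Conclusion.** The point holds as a should-fix. The rule is indifferent to where gaps fall, its denominator is undefined, and the sections conflict on adjacency. On the schedule alone, a participant can be complete with 184 days unobserved, Day 180 included, if the 75% is taken up to the stop. Under a fixed 31, a fully attending participant can fail at 74%. A participant with washed-out levels at Days 450 and 540 can fail at 93.5% collection. Each case changes the primary count by one of ten.

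The counts rest only on the listed time points and on which reading of the denominator and of *consecutive* is applied. How often such cases occur cannot be derived from the documents.

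Illustrative calculations on assumed declining profiles, with Days 90 to 270 missed, gave AUC errors from -13% to +27% in one set and -37% to +44% in another. T>MEC errors ran from -54 to +72 and from -73 to +92 days. They vary with the assumed shape and with log or linear interpolation, and mostly describe a gap the rule would not accept. They show that interpolating over such a hole is unsafe; they are not estimates for this trial.

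**What to change.** Adopt these as analysis definitions, worded identically in 4.2.1, 5.3.1, 10.3, 10.4.2 and 10.5, and fixed before database lock:

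1. Washout is two successive collected samples below 0.1 ng/mL, separated by a stated minimum interval by actual date, with no level of 0.1 or more between them. A missed draw does not break the sequence. Reconcile 7.3.6 and 7.3.9 with this definition.
2. The 75% denominator is the number of points scheduled up to the participant's washout or Day 540. State whether the Final Visit draw counts.
3. The Day 180 draw is required for the Day 180 endpoint in 4.2.3, as the interim already requires it. Where a gap spans the 1.33 ng/mL crossing, report T>MEC as interval-censored and flag the AUC.

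A maximum-gap limit for completers is optional. The documents give no basis for a particular length, so that limit, like the minimum interval in item 1, is the sponsor's choice.

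The cost is protocol and SAP wording. Item 3 may lower the number evaluable at Day 180. Items 1 and 2 may raise the completer count, so they should be settled without reference to who would be gained. Item 2 by itself still admits the 184-day gap; item 3 is what keeps such a profile from being read as fully observed.

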#### 4.2.2 Secondary Endpoints

- Detailed PK characteristics of the product.
- The collection of safety information and AEs information over 540 days in participants treated with the OLANI.

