#### 4.2.4 Secondary Efficacy Endpoints:

- Mean Cmax, Tmax, AUC for naltrexone blood level
- Mean T>MEC for naltrexone, where MEC = 1.33 ng/mL
- Mean Cmax, Tmax, AUC for 6β-naltrexol blood level
- Frequency of AEs and SAEs

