#### 7.3.8 Unscheduled Visit

It is anticipated that some participants may miss or be delayed to some of their appointments. Every effort will be made to obtain blood samples at the scheduled dates, but blood samples will be accepted if they are taken late, with allowances made in the statistical analysis for this. Participants who miss appointments will be contacted by phone to encourage them to return for as many appointments as possible. However, some dropouts are also anticipated so additional participants will be recruited to get the correct totals for analysis.

Participants will be asked to complete the following; vital signs, concomitant medication review, wound site/implant site assessment and AE monitoring (see Table 7-1). Additional assessments performed at Unscheduled visits are at the discretion of a study physician.

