#### 10.4.2 Analysis of the Primary Endpoint

Participants who submitted at least 75% valid pharmacokinetic blood samples including 2 consecutive monthly naltrexone blood levels recorded at <0.1 ng/mL will be analyzed.

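### Time to C0 is a primary-objective parameter with no definition, endpoint or named analysis, and the planned primary analysis set would tend to make it too short

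*Combined protocol and SAP*

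**What the plan says.** The primary objective (3.1, repeated in the Protocol Summary) is "To characterize the pharmacokinetic profile" of two implants through Cmax, Tmax, AUC, T>MEC (MEC 1.33 ng/mL) and Time to C0 for naltrexone. The same section describes the plasma concentrations as the primary outcomes from which these are derived.

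The primary endpoint (4.2.1) is "The collection of at least 75% pharmacokinetic blood time points", and it continues "including 2 consecutive monthly naltrexone blood levels recorded at <0.1 ng/mL, in 10 participants". PK itself is ranked lower: "Detailed PK characteristics of the product" is a secondary endpoint (4.2.2), and 4.2.4 lists "Mean Cmax, Tmax, AUC for naltrexone blood level" and mean T>MEC among the secondary efficacy endpoints. A separate primary efficacy endpoint (4.2.3) is the proportion who tolerate the implant and hold at least 1.33 ng/mL to Day 180 or later.

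On analysis:
- 10.3 assesses primary outcomes in participants with at least 75% of applicable time points.
- 10.4.2 adds observed washout. Its one sentence ends "2 consecutive monthly naltrexone blood levels recorded at <0.1 ng/mL will be analyzed" and gives no statistic, estimator or success rule.
- 10.4.1 summarises PK parameters, without naming any, by mean, SD and CV.
- 10.4.3 names Cmax, Tmax, AUC to infinity and time above 1.33 ng/mL. It does not name Time to C0.
- 10.4.11 rules out exploratory analysis.

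**The concern.** Time to washout is what the long follow-up is for. Section 4.1 continues PK sampling until two consecutive monthly levels are below 0.1 ng/mL, and the change history for Version 0.6 gives defining the time to undetectable naltrexone as the reason for extending the study. The protocol therefore collects the event that would define Time to C0 but does not plan to estimate when it happens.

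If the plan is followed literally, one of two things results. Either this part of the primary objective is not estimated, or an analyst fills the gap with the default mean and SD among participants who reached washout. That set leaves out participants who left while naltrexone was still measurable, who are informative about slow washout. The study's PK data are meant to inform a later bioequivalence study (2.2), so a washout time that is too short would be carried forward.

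**Working it through.** **1. The plan's own figure.** Section 5.3.1: 20 recruited, 50% expected to complete. 10 / (1 − 0.5) = 20, so the figure reproduces. Section 10.2 states no hypothesis, and no alpha, power or SD is given, so no power formula applies. Taking completion as binomial, the chance of at least 10 of 20 completers is 0.588 at exactly 50% (0.245 at 40%, 0.873 at 60%, 0.983 at 70%).

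**2. What the primary endpoint requires.** Section 3.1 lists 6 hourly and 25 later time points, 31 in all to Day 540. 0.75 × 31 = 23.25, so 24 samples are needed and 7 may be missed. Each of 10 participants also needs two assayed levels below 0.1 ng/mL, so at least 10 × 2 = 20 assay results. No value of Cmax, Tmax, AUC, T>MEC or Time to C0 enters the count.

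**3. Where each objective parameter goes.**

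| Parameter (3.1) | Primary endpoint (4.2.1) | Named in another endpoint (4.2.2 to 4.2.5) | Named analysis (10.4.1 to 10.4.3) |
|---|---|---|---|
| Cmax | no | yes (4.2.4) | yes (10.4.3) |
| Tmax | no | yes (4.2.4) | yes (10.4.3) |
| AUC | no | yes (4.2.4) | yes (10.4.3) |
| T>MEC | no | yes (4.2.4) | yes (10.4.3) |
| Time to C0 | no | no | no |

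None of the five is in the primary endpoint. One of the five has no named endpoint or analysis anywhere.

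**4. What is left undefined.** Undetectable is set at below 0.1 ng/mL (10.5; Table 7-1, footnote 8), but this is not tied to C0; the Version 0.13 change note puts the quantification limit at 0.02 ng/mL. Nor is it stated whether the time is that of the first or the second low sample. Monthly visits are 30 days apart, so that choice alone moves each value by about 30 days.

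**5. Why the time is interval-censored.** Washout falls somewhere between the last level at or above 0.1 and the first confirmed level below it. With monthly visits ±10 days (Table 7-1), two adjacent visits lie 30 − 20 = 10 to 30 + 20 = 50 days apart. One missed draw makes the nominal gap 60 days, and 7.3.5 accepts that draws may be missed because of COVID-19.

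**6. Direction of the bias.** To be counted, a participant must be retained until the second low sample. First low level at Day 240 requires retention to Day 270; first low level at Day 510 requires retention to Day 540, twice as long (540 / 270 = 2). The documents give no distribution of washout times, so the size can only be illustrated. Assume half the participants are of each kind, all non-completion is departure at a constant rate unrelated to washout speed, and 50% complete overall. Let r be retention to Day 270, so retention to Day 540 is r². Then (r + r²) / 2 = 0.5, giving r = 0.618 and r² = 0.382.

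- True mean: (240 + 510) / 2 = 375 days.
- Mean among completers: 0.618 × 240 + 0.382 × 510 = 343 days.
- Shortfall: about 32 days.

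If everyone washed out at the same visit, the shortfall would be 0. The range 0 to 32 days shows direction and order of size only; it is not a forecast.

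**The case against.** The strongest reply is that the endpoint is more than a tally of blood draws, and that is right. A reader might infer that the trial could meet its primary endpoint with no PK result, or that the count is uninformative about the product. The text does not support either: 4.2.1 requires assayed washout in each of 10 participants, so ten fully sampled participants whose levels never fell below 0.1 ng/mL would fail it. Section 4.2.3 adds a product-level PK result labelled primary, although it is a yes/no at 1.33 ng/mL and does not estimate T>MEC.

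The ranking of Cmax, Tmax, AUC and T>MEC is also mostly labelling. There is no hypothesis (10.2) and no multiplicity adjustment (10.4.9), and these parameters are calculated, summarised and plotted whatever their rank. A completion-based endpoint is defensible in a pilot.

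A reader might also take 7.3.8, "some dropouts are also anticipated so additional participants will be recruited to get the correct totals for analysis", as permission to keep enrolling until the count is met. It can equally refer to recruiting 20 to obtain 10 (5.3.1), so open-ended recruitment is not established.

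Finally, "Detailed PK characteristics of the product" in 4.2.2 and the general summary rule in 10.4.1 could be stretched to cover Time to C0. Neither names or defines it, and a mean and SD do not handle participants without observed washout. That part of the reply does not stand.

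**Conclusion.** The point holds for Time to C0. It is one of five parameters in the primary objective, with no definition, no named endpoint and no named analysis, and 10.3 with 10.4.2 confine the primary analysis to a set that half of those enrolled are expected not to enter. A mean in that set would tend to be too short. The direction rests on departure being unrelated to washout speed; if participants with fast washout leave more often, or implants are removed, it could differ. The size cannot be computed from the documents.

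The mismatch between 3.1 and 4.2.1 is real but secondary. The count can be met without estimating any objective parameter, yet four of the five are planned for elsewhere. This is a recommended correction to be made before database lock; it does not invalidate the study.

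**What to change.** 1. Define Time to C0 in 3.1 and the Protocol Summary as the time from implantation to the first of two consecutive monthly naltrexone levels below 0.1 ng/mL, and say how a missed draw between two low levels is treated.
2. Add it to 4.2.4 and 10.4.3.
3. Estimate it in all implanted participants, and state in 10.3 and 10.4.2 that this analysis is exempt from the 75% and observed-washout restrictions. Without that exemption, the early leavers who should be censored would be excluded instead.
4. Report an interval-censored (Turnbull-type) median with a 95% CI. Right-censor participants who leave before confirmed washout at their last level at or above 0.1 ng/mL. State how implant removal is handled in this analysis.
5. As a lesser change, name the PK parameters as primary in 4.2.1 and the Protocol Summary, and keep the 75%-in-10 rule as a feasibility target in 10.5.

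No new data, visits or sample-size change are needed. The cost is a little more analysis work and a wider, possibly longer, estimate of washout time. With item 5, the primary result is also no longer a simple yes/no count.
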